### **Patient Input**

After each procedure was performed (TA or VR), the participants were asked to evaluate the degree of pain that they experienced using the Wong-Baker Faces Pain-rating Scale (W-BFPS). Official permission was issued from the Wong-Baker FACES Foundation.

Additionally, each participant was also asked to state his/her preference of delivery system for future injections.

### **Risk of bias**

To avoid the risk of bias, the following were considered:

- All participants were blinded to the order of the technique to be used.
- Both procedures were coded and blinded to the one who did the analysis.
- Both types of procedures were performed in one session by the same operator to avoid an inter-operator variability influence.
- Special attention was given to keep the syringe out of their line of sight.
- Regarding communication with the participants, the words (*injection shot, pain, and hurt*) were not used to avoid increasing stress or fears.

## **Statistical Analyses**

The normality of the heart rates observed was calculated and was observed to be within acceptable limits of Kurtosis and Skew. Therefore, parametric tests were used to analyze differences in heart rate. Given the subjective nature of Wong-Baker faces pain-rating scale (W-BFPS), non-parametric tests were used to analyze differences in W-BFPS.

The paired *t* test was used to compare the heart rates of the individuals between the two methods. The Wilcoxon Sign rank test was used to compare the W-BFPS between the two methods. The spearman's correlation was used to check the association between W-BFPS and heart rate for each procedure. All tests were performed at  $p<0.05$ .

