## **Materials and method**

The study was performed in accordance with the Declaration of Helsinki. Twenty-one adult volunteers visiting the Riyadh Elm University dental hospital participated in the study, with an age range from 22 to 59 years. The procedures were explained to the volunteers in detail and an informed written consent form were signed by each participant. IRB Approval no. RC/IRB/2019/321 was obtained from the Research Center at Riyadh Elm University, Riyadh, Saudi Arabia.

The study was conducted according to the design of split-mouth randomized controlled double-blinded trials. Each participant was randomly allocated to first receive the conventional injection technique under the influence of either *topical anesthesia* or *virtual reality* at the area of the upper second premolar on one side; and then the other procedure on the contralateral tooth after an average of a 10-minute interval. Since it was a split-mouth design, each participant served as his/her own control.

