**Table 3: Significance of difference in heart rate before and after giving the injection for each type of procedure**

		Paired Differences					t*	Sig. (2-tailed )		
		Mean	Std. Deviation	Std. Error Mean	95% Confidence Interval of the Difference					
					Lower	Upper				
With VR	Heart Rate Before - Heart Rate After	1.80952	4.02019	.87728	-.02044	3.63949	2.063	.052		
With TA	Heart Rate Before - Heart Rate After	1.42857	6.20138	1.35325	-1.39426	4.25141	1.056	.304		

\* Calculated using the paired t test Differences are not statistically significant

The patients recorded lower heart rates while in VR than in Topical anesthetic as mentioned earlier. This was true both before and after the dental injections. However, the paired *t* test found the differences to be statistically insignificant both before and after dental injections. While when gender differences were observed it was seen that the females had a higher heart rate compared to the males in each of the four situations. It was observed that these differences were statistically significant for TA-before, VR-before and VR-after (Table 4).

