**Table 4 – Differences in Heart Rate according to Gender for each procedure**

	Gender	Mean	Std. Deviation	t*	Sig
Heart Rate Before (VR)	Male	73.4000	6.09554	-2.117	0.048**
	Female	81.6364	10.8284		
Heart Rate After (VR)	Male	73.9000	6.62403	-1.102	0.311
	Female	77.7273	9.92059		
Heart Rate Before (TA)	Male	74.9000	9.65459	-2.118	0.048**
	Female	85.4545	12.7778		
Heart Rate After (TA)	Male	74.1000	7.29459	-.2.369	0.029**
	Female	83.4545	10.3572		

\*\*Differences are significant at  $p<0.05$

A paired t test comparing the change in heart rate per procedure with the gender of the participants, showed no significance for both genders.

The patient's experience of pain with each group was measured using Wong-Baker Faces Pain-rating Scale (W-BFPS). The Wilcoxon Sign Rank test showed that while 10 of the 21 participants had a higher W-BFPS with TA when compared to VR, 5 of the 21 reported a worse experience with VR when compared to TA. There were six individuals who reported the same experience with both procedures (Table 5). These differences were however not significant ( $Z=1.662$ ,  $sig= 0.096$ )

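### The between-method heart-rate comparison uses raw pulse and never reports the VR-versus-TA difference in change (0.38 bpm); the randomised order is neither reported nor examined

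*Combined protocol and SAP*

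**What the plan says.** Order was the randomised element. In Materials and method each participant was "randomly allocated to first receive the conventional injection technique" under one method, "and then the other procedure on the contralateral tooth after an average of a 10-minute interval". The Risk of bias section adds: "Both types of procedures were performed in one session by the same operator". Pulse was recorded before and after each procedure (the TA and VR procedure sections).

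For the comparison of methods, Statistical Analyses states that the paired t "test was used to compare the heart rates of the individuals between the two methods", and it assigns the Wilcoxon signed-rank test to the Wong-Baker pain score. Neither test is described with a term for order or for pre-procedure pulse.

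In the Results, Table 3 gives the before-minus-after change within each method. The text after it says the paired t test "found the differences to be statistically insignificant both before and after dental injections", without an estimate, interval or p-value for either comparison. The same text says: "The patients recorded lower heart rates while in VR than in Topical anesthetic as mentioned earlier". One sentence after Table 4 returns to change: "A paired t test comparing the change in heart rate per procedure with the gender of the participants, showed no significance for both genders". It carries no figures. The number of participants in each order is not given.

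**The concern.** One aim is to compare anxiety control between VR and TA, and pulse is the only reported measure that bears on it. With a reading before and after each procedure, the natural contrast is the difference between methods in the change. It is not reported. The reader has two substitutes, and neither answers the question.

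- **Two within-method tests.** Set side by side, p = 0.052 and p = 0.304 suggest that VR nearly lowered pulse and TA did not. A difference between two p-values is not a test of the difference between methods.
- **A raw post-procedure comparison.** It ignores a pre-procedure reading that was already collected and is strongly correlated with the outcome. Most of the post-procedure gap was there beforehand. The text nevertheless describes lower rates during VR and says this held before the injection too, although the VR procedure section takes that reading before it describes fitting the headset.

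Separately, two injections about 10 minutes apart in one session are a setting in which a period effect is possible. With no count or result by order, a reader cannot judge whether one mattered, for pulse or for the pain score that the null hypothesis concerns.

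**Working it through.** **Inputs.** n = 21. Mean pulse from Table 1: VR 77.7143 before and 75.9048 after; TA 80.4286 before and 79.0000 after. SDs in the same order: 9.64957, 8.53173, 12.35950, 10.02497. Mean fall and its SD from Table 3: VR 1.80952 (4.02019); TA 1.42857 (6.20138).

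**1. Reproduce Table 3.** t = mean / (SD/√21), 20 degrees of freedom.
- VR: 1.80952/0.87728 = 2.063, p = 0.052, CI -0.020 to 3.639.
- TA: 1.42857/1.35325 = 1.056, p = 0.304, CI -1.394 to 4.251.

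Both agree with the table.

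**2. Gaps between methods (TA minus VR).**
- Before: 80.4286 - 77.7143 = 2.71 bpm.
- After: 79.0000 - 75.9048 = 3.10 bpm.
- Share already present before: 2.714/3.095 = 88%.

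**3. Difference in change.** 1.80952 - 1.42857 = 0.38 bpm, a slightly larger fall with VR. As a cross-check from Table 4, the VR-minus-TA difference in fall is -1.30 in the 10 men and +1.91 in the 11 women; (10 × -1.30 + 11 × 1.91)/21 = 0.38.

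**4. Its precision.** SD = √(4.02019² + 6.20138² - 2r × 4.02019 × 6.20138), where r is the correlation between the two changes. It is not reported, so a range is shown. CI = 0.38 ± 2.086 × SD/√21.

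| assumed r | SD | 95% CI (bpm) | p |
|---|---|---|---|
| -1 | 10.22 | -4.27 to 5.03 | 0.87 |
| 0 | 7.39 | -2.98 to 3.75 | 0.82 |
| 0.5 | 5.45 | -2.10 to 2.86 | 0.75 |
| 1 | 2.18 | -0.61 to 1.37 | 0.43 |

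The smallest possible p is 0.43.

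**5. How informative the pre-procedure reading is.** Implied before-after correlation = (SD_before² + SD_after² - SD_change²)/(2 × SD_before × SD_after).
- VR: (93.11 + 72.79 - 16.16)/164.66 = 0.91.
- TA: (152.76 + 100.50 - 38.46)/247.81 = 0.87.

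**6. Order.** A period effect adds to the VR-minus-TA difference in one order and subtracts in the other, so the plain mean carries (n1 - n2)/21 of it: 1/21 = 5% at 11:10 and 7/21 = 33% at 14:7. Both splits are illustrations; the actual one is not given. Adjusting for order multiplies the variance by 441/(4 × n1 × n2): 441/440 = 1.002 at 11:10 and 441/392 = 1.125 at 14:7.

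**The case against.** The null hypothesis concerns pain, not pulse. The 0.38 bpm follows from Table 3 by subtraction, so only its interval is really missing. The sentence after Table 4 may describe a between-method test of change within each gender, in which case change was not wholly ignored. The second pre-procedure reading follows the first injection and may hold carry-over, so neither the change contrast nor the post-procedure contrast is plainly the correct one. A paired test without a period term is a valid and common choice for a within-person design.

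Most of this stands and limits the weight of the point. It does not supply the missing contrast: the gender sentence is ambiguous and has no figures, and the interval cannot be derived without the correlation between changes.

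Two stronger readings are tempting, and the document supports neither.

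- **That the tests are invalid because they ignore order.** If order was set by an independent fair coin (the method is not stated), the signed-rank test keeps its 5% level. No period effect and no unequal split is documented.
- **That the heart-rate conclusion is settled under any analysis.** Step 4 settles it for the plain change score only. As a constructed counter-example, take assumed VR-TA correlations of 0.55 before and 0.67 after, with 0.56 between VR-before and TA-after and 0.45 between VR-after and TA-before. These fit the SDs and Table 3, and both raw tests remain non-significant. Regressing the after-difference on the before-difference then gives a method effect of 1.19 bpm (SE 0.32, p = 0.002). That is a contrived case, not an expectation; it shows only that the adjusted result cannot be inferred.

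**Conclusion.** The point holds as a minor one. The between-method contrast of pulse change is not reported, the within-method p-values cannot stand in for it, and 2.71 of the 3.10 bpm post-procedure gap was present before the procedures. The difference in change is 0.38 bpm and is non-significant whatever the correlation between the two changes; the width of its interval depends on that unreported correlation. Whether a baseline-adjusted or order-adjusted analysis would agree cannot be known from the document. On order, the firm defect is the missing count per order. No error in the pulse or pain-score tests is shown on that account.

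**What to change.** - **Pulse.** Report the paired VR-versus-TA difference in pulse change with its 95% CI as the between-method heart-rate comparison. Show beside it the post-procedure contrast without the baseline term, with its estimate and CI, because the second pre-procedure reading comes after the first injection.
- **Order.** State the number of participants in each order. If each participant's order was recorded, add sensitivity analyses beside the existing tests: order as a factor for pulse and, for the pain score, a Wilcoxon rank-sum test of period-1-minus-period-2 differences between the two order groups. Make the latter exact or tie-corrected, since "There were six individuals who reported the same experience with both procedures".
- **Labelling and wording.** Mark all of these as added after the results were known. Reword the text after Table 3 so that the pre-procedure difference is not presented as arising during VR.

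**Cost.** The change contrast needs only readings already held. The order analyses depend on a record of order, which the document does not confirm exists. For pulse they use one degree of freedom and lose a little precision if there is no period effect: variance up 0.2% at 11:10 and 12.5% at 14:7.

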# **Cover letter**

## **Comparison between the Analgesic Effectiveness of Virtual Reality and Topical Anesthesia: A Clinical Study**

**Date of document: April 28th 2021**

## **Aim**

The aims of the study are to compare the analgesic and anxiety control effectiveness of virtual reality (VR) and topical anesthesia (TA) gel during administration of local anesthesia in adult dental patients, and to determine which approach the patients preferred to reduce pain of dental injections.

The null hypothesis was that there will be no significant difference between the effect of virtual reality compared to that of topical anesthesia gel in reducing pain during administration of local anesthesia injections in adult dental patients.

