## **Sample Power Calculation**

Sample power was calculated using the G-Power sample power calculator (Universtat Kiel, Kiel, Germany). Given the split mouth study design, an effect size of 0.75 (high effect size) was assumed and for a power of 0.95, the total number of participants was determined as 21.

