**Table 5: Comparisons and Ranking of W-BFPS**

		N	Mean Rank	Sum of Ranks	Z*	Sig
W-BFPS - VR	Negative Ranks	5 a	6.50	32.50	1.662	0.096
	Positive Ranks	10 b	8.75	87.50		
	Ties	6 c				

	Total	21				
--	-------	----	--	--	--	--

a. W-BFPS - TA < W-BFPS – VR

[figure not shown]
b. W-BFPS - TA > W-BFPS – VR

c. W-BFPS - TA = W-BFPS – VR

\*calculated using the Wilcoxon Sign Rank test

Differences are not statistically significant

In contrast to the heart rate and W-BFPS reading of pain level, when patients were asked which method they preferred, a significant majority (Chi square = 14.124, p=0.021) reported that they preferred the VR to Topical Anesthesia (Fig 1).

**Fig 1:** Stated preference of procedure by the population

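### Every test is judged at 0.05 with no named primary, and three gender differences in raw heart rate are called significant although they answer no stated aim and none survives adjustment.

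*Combined protocol and SAP*

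**What the plan says.** The Aim section sets out to "compare the analgesic and anxiety control effectiveness of virtual reality (VR) and topical anesthesia (TA) gel" and to establish which approach patients prefer. The three aims are not ranked. The only null hypothesis is about pain: "no significant difference between the effect of virtual reality compared to that of topical anesthesia gel in reducing pain".

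Sample Power Calculation does not identify a primary either. It says "an effect size of 0.75 (high effect size) was assumed" and "for a power of 0.95, the total number of participants was determined as 21", without naming the outcome.

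Statistical Analyses lists three analyses: a paired t test for heart rate ("test was used to compare the heart rates of the individuals between the two methods"), a Wilcoxon signed-rank test for the Wong-Baker score (W-BFPS), and Spearman correlations for each procedure. It closes with "All tests were performed at" p<0.05. It mentions no gender comparison and no test of preference.

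The Results, in the text after Table 3, report male-female differences in raw heart rate: "It was observed that these differences were statistically significant for TA-before, VR-before and VR-after (Table 4". Table 4 gives p=0.048 (VR-before), 0.311 (VR-after), 0.048 (TA-before) and 0.029 (TA-after), and stars the first, third and fourth. After Table 5, "a significant majority (Chi square = 14.124, p=0.021) reported that they preferred the VR to Topical Anesthesia".

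**The concern.** A flat 0.05 for every test, with nothing ranked, gives a comparison added at the reporting stage the same standing as the test of the stated hypothesis. That has happened with the gender comparisons. They are absent from the Statistical Analyses section, they compare the sexes rather than the two methods, and they answer none of the three aims. Yet they carry significance flags, while the pain comparison and the between-method heart-rate comparisons are reported as not significant. The gender analysis closest to treatment response, change in heart rate by gender, is also reported as not significant.

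What is at stake is the standing of three reported significance claims, one of which is attached to the wrong comparison in the text. The answer to the pain hypothesis is not at stake.

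**Working it through.** **1. Reproduce Table 4.** Inputs: the Table 4 means and SDs, with 10 men and 11 women (Results, descriptive statistics). Pooled two-sample t test on 19 df: SE = s_p × √(1/10 + 1/11), and 95% CI = difference ± 2.093 × SE.

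| Comparison | Female − male (bpm) | SE | t (absolute) | p recomputed | p printed | 95% CI |
|---|---|---|---|---|---|---|
| VR-before | 8.24 | 3.89 | 2.117 | 0.0477 | 0.048 | 0.1 to 16.4 |
| VR-after | 3.83 | 3.72 | 1.028 | 0.317 | 0.311 | −4.0 to 11.6 |
| TA-before | 10.55 | 4.98 | 2.118 | 0.0476 | 0.048 | 0.1 to 21.0 |
| TA-after | 9.35 | 3.95 | 2.369 | 0.0286 | 0.029 | 1.1 to 17.6 |

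The three starred results reproduce. For VR-after the printed t is −1.102, against −1.028 here (Welch: −1.048, p=0.309). It is far from 0.05 either way.

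**2. Text against table.** The text lists TA-before, VR-before and VR-after. The table stars TA-before, VR-before and TA-after. The recomputation agrees with the table.

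**3. Adjust over the four gender tests.** Ordered printed p-values: 0.029, 0.048, 0.048, 0.311.
- Holm: 4 × 0.029 = 0.116; 3 × 0.048 = 0.144; 2 × 0.048 = 0.096, raised to 0.144; 0.311.
- Hochberg: the three smaller values all become 2 × 0.048 = 0.096.
- Hommel: smallest 0.072.
- Benjamini-Hochberg: the three smaller values all become 0.048 × 4/3 = 0.064.

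None is at or below 0.05.

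**4. Allow for correlation.** Holm is conservative when tests are positively correlated, as these are. The before-after correlation follows from Tables 2 and 3 as r = (s_b² + s_a² − s_d²)/(2 s_b s_a):
- VR: (93.11 + 72.79 − 16.16)/164.66 = 0.91
- TA: (152.76 + 100.50 − 38.46)/247.81 = 0.87

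The documents do not give the correlation between methods. Assuming 0.3 to 0.9 and simulating the four tests under no gender difference, the chance of at least one p<0.05 is about 13% down to 10% (independence: 1 − 0.95⁴ = 18.5%). The adjusted smallest p is then about 0.08 down to 0.06, still above 0.05.

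**5. Overall count, as illustration only.** 2 before-after + 2 between-method + 4 gender + 2 gender-by-change + 1 Wilcoxon + 2 Spearman + 1 chi-square = 14. If all were independent and every null true, 1 − 0.95¹⁴ = 0.51; without the two Spearman tests, for which no result is reported, 1 − 0.95¹² = 0.46. The correlations in step 4 show that independence does not hold.

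**6. Preference.** A chi-square of 14.124 on 1 df gives p=0.00017, not 0.021, and no df from 1 to 7 gives 0.021. If preference and between-method heart-rate change form the secondary family, Holm gives preference at most 2 × 0.021 = 0.042 on the printed p, or 2 × 0.00017 = 0.0003 on the printed statistic. Both are below 0.05.

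**The case against.** The strongest reply is that little depends on this. The only stated null hypothesis concerns pain, so pain is the implied primary. Its test is reported as not significant (p=0.096), and no adjustment can alter that. The gender results feed no aim, and the document has no conclusions section that draws on them. All of this stands, and it limits the point to the gender claims and to how the endpoints are ranked. It does not justify significance flags on comparisons outside the analysis section.

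It can also be said that naming a primary now is retrospective. That is true. The designation must be labelled as made after the results were known. It follows the document's own hypothesis and selects a non-significant result, so it favours neither method.

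Four stronger readings are tempting, and the documents do not support them:
- **That the preference finding also fails adjustment.** Step 6 shows it does not over the two secondary endpoints. The disagreement between its statistic and its p-value is a separate error.
- **That every result called significant was unplanned.** Preference is a stated aim, and its collection is described under Patient Input. Only its test is unspecified.
- **That the trial ran a 51% risk of a false positive.** That figure needs independence, and the count of 14 is itself soft: the gender-by-change sentence could mean two tests or four.
- **That the gender differences are shown to be chance.** Failing adjustment shows only that the evidence falls short of a significance claim.

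**Conclusion.** The concern holds for the gender comparisons. Three of four are declared significant under a blanket 0.05 rule, outside the listed analyses and outside the aims. Over the four tests none survives Holm, Hochberg, Hommel or Benjamini-Hochberg. For VR-before and TA-before, the unadjusted intervals start only about 0.1 bpm above zero. The text's list is also wrong for one of the three.

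This rests on taking all four comparisons in Table 4 as the family. Hochberg or Benjamini-Hochberg applied to the three starred values alone would keep them, since the largest is 0.048, but that family could be chosen only after seeing the results. The allowance for correlation rests on an assumed between-method correlation of 0.3 to 0.9.

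The answer on pain is unchanged. Whether preference is significant should be left open until its p-value is recomputed from the counts.

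**What to change.** - Label the gender comparisons post hoc and exploratory. Report female-minus-male differences with 95% confidence intervals (step 1), remove the double-asterisk flags and their footnote from Table 4, and remove the significance statement from the text after Table 3.
- Reconcile the VR-after/TA-after mismatch between that text and Table 4, and check the printed t and p for VR-after.
- In Statistical Analyses, state that the between-method W-BFPS comparison is treated as primary at two-sided 0.05 because it tests the only stated null hypothesis. Say that this designation was made after the results were known.
- Treat between-method change in heart rate and preference as secondary, Holm-adjusted over those two. The between-method test of change is not reported and needs the participant data.
- Before adjusting, recompute the preference p-value from the counts. State the test and its degrees of freedom.

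The cost is wording plus two short calculations on existing data. The downside is the loss of three nominal gender flags that answer no stated aim.
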